9.4. ANTICIPATED ADVERSE EVENT

Co-morbidities and symptoms/laboratory/physiological deviations normally associated with pre-existing conditions (e.g., diabetes, ASHD, other CV conditions, pneumonia, dialysis shunt problems, neurologic deficits) are considered “anticipated adverse reactions.” The investigator is required to take special care in differentiating concomitant illness events from those related to the therapy by use of subject history, relationship to treatment time and cartridge integrity, and other characteristics of clinical circumstances present at the time of the adverse experience, including drug interactions of concomitant medications and effects of surgical and/or medical procedures.

Adverse events associated with CRRT or underlying critical illness are also to be considered “anticipated”. Such events include but are not limited to the list in **Section 9.1** above.

Any questions as to the expectedness of an adverse event will be discussed with Drs [name] and [name]. Final review and assessment will be made by the Sponsor-Investigator, [name] and the DSMB.

9.5. CAUSALITY

All enrolled subjects must have all AEs assessed for causality (probability that the AE may have been caused by the study treatment) by the Principal Investigator. The following definitions for causality assessment will be used in this study:

9.5.1. DEFINITELY RELATED

A clinical event, including a significant change in a laboratory test, that occurs in a plausible time relationship to the SCD treatment or other protocol-required activity, and which cannot be explained by concurrent disease or other drugs, chemicals, or procedures and that follows a clinically reasonable response upon withdrawal of the SCD treatment.

9.5.2. PROBABLY RELATED

A clinical event, including a significant change in a laboratory test, that occurs within a reasonable time sequence in relationship to the SCD treatment or other protocol-required activity that is unlikely to be attributed to concurrent disease, other drugs, chemicals, or procedures, and that follows a clinically reasonable response upon withdrawal of the SCD treatment.

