9.5.3. POSSIBLY RELATED

A clinical event, including a significant change in a laboratory test, that occurs within a reasonable time sequence in relationship to the SCD treatment or other protocol-related activity that could also be explained by concurrent disease, drugs, chemicals, or procedures. The clinical course after withdrawal of the SCD treatment may be unclear with respect to the contribution of the SCD treatment to the AE.

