9.5.4. UNRELATED

An AE, including a significant change in a laboratory test, that occurs with a temporal relationship to the SCD treatment or protocol-required activity that makes an association with the SCD treatment or study activity improbable, and in which other drugs, procedures or underlying disease(s) provide likely explanation.

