9.8. SPONSOR INVESTIGATOR RESPONSIBILITIES

The Sponsor-Investigator will review documented serious adverse effects and abnormal test findings to determine 1) if the abnormal test finding should be classified as an adverse effect; 2) if there is a reasonable possibility that the adverse effect was caused by the investigational device or, if applicable, other study treatment or diagnostic product(s); and 3) if the adverse effect meets the criteria for a *serious adverse effect*.

In accordance with 21 CFR Part 812.150(a)(1) and (b)(1), the sponsor shall promptly report the results of an evaluation of any serious and unanticipated adverse device effect to FDA, the University of Michigan IRBMED and participating investigators (if any) as soon as possible, but not later than 10 working days after the sponsor first receives notice of the effect. Thereafter, the sponsor shall submit such additional reports concerning the effect as the FDA requests. Complications and non-serious or anticipated adverse events should be documented and tabulated but need not be submitted by the sponsor to the FDA as individual reports.

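### Sections 9.5.1 and 9.5.2 require a response to SCD withdrawal, so as written deaths, irreversible events and post-treatment SAEs cannot be rated above Possibly Related, and some fit no level

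*Combined protocol and SAP*

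**What the plan says.** Section 9.5 sets the scope: "All enrolled subjects must have all AEs assessed for causality". Section 9.2 counts deaths and lasting disability as serious adverse events. Section 9.7.2 records SAEs to Day 60 after enrollment, while Section 6.5 limits SCD treatment to 240 hours.

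The four levels are:

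- **Definitely Related (9.5.1):** plausible timing, no explanation from disease, drugs, chemicals or "procedures and that follows a clinically reasonable response upon withdrawal of the SCD treatment".
- **Probably Related (9.5.2):** reasonable timing, other causes unlikely, "and that follows a clinically reasonable response upon withdrawal of the SCD treatment".
- **Possibly Related (9.5.3):** reasonable timing, for an event "that could also be explained by concurrent disease, drugs, chemicals, or procedures". No withdrawal response is needed: "The clinical course after withdrawal of the SCD treatment may be unclear with respect to the contribution of the SCD treatment to the AE".
- **Unrelated (9.5.4):** timing that "makes an association with the SCD treatment or study activity improbable", with another likely explanation.

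Neither of the top two definitions says where assessable or where applicable, and no other section waives the condition.

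**The concern.** A response to withdrawal is useful evidence when an event is reversible and the device is removed while the event is still going on. As a mandatory condition, it bars the events for which no such response can be observed, and these include the most serious ones.

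Safety is the primary objective. The study enrolls up to 10 children with no concurrent control arm, so case-by-case attribution is one of the main ways to separate device harm from background illness. Section 11 asks the DSMB to assess the relationship of adverse events.

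Relatedness ratings also feed later safety statements. Section 2.5.2 reports that no SAE in the earlier pivotal trial was rated definitely device related. Section 1.2 supports treatment up to ten days by saying that prior studies showed no device-related adverse events, although Table 3 in Section 2.4.2 lists 12 events possibly related and 1 definitely related to study therapy. The scale used in those trials is not given, and Table 3 concerns study therapy rather than the device alone. The comparison therefore shows only that events rated possibly related need not appear in a summary sentence.

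**Working it through.** The document gives no figure on this point, so there is none to reproduce. The check reads the definitions as conditions and applies them to cases.

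**Step 1: the conditions.** Let T be acceptable timing and W a clinically reasonable response on withdrawal.

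- Definitely = T, and no other explanation, and W.
- Probably = T, and other causes unlikely, and W.
- Possibly = T, and another cause could explain the event. W is not required.
- Unrelated = association improbable, and another likely explanation.

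**Step 2: cases in which T is met.**

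| Event | Can W be observed? | Another cause could explain it | Other causes unlikely | No other explanation |
|---|---|---|---|---|
| Reversible, SCD withdrawn during the event, improves | Yes | Possibly | Probably | Definitely |
| Death on SCD | No | Possibly | Possibly at most | No level |
| Irreversible injury | No recovery to observe | Possibly | Possibly at most | No level |
| Resolves while SCD continues | No, SCD was not withdrawn | Possibly | Possibly at most | No level |
| SAE starting after SCD is off | No, nothing left to withdraw | Possibly | Possibly at most | No level |

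In the third column the clause changes nothing. It changes the outcome only in the last two columns. In the fourth, Possibly is available only if an unlikely cause still counts as one that could explain the event. In the last, Definitely and Probably fail on W, Possibly fails because no other explanation exists, and Unrelated fails because the association is not improbable.

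A related gap: 9.5.1 and 9.5.2 also cover events tied to other protocol-required activity, but the only withdrawal they test is that of SCD.

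**Step 3: how much SAE follow-up is off device.**

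- Maximum treatment: 240 / 24 = 10 days.
- SAE collection: 60 days from enrollment.
- Off device after a full course: 60 − 10 = 50 days, and 50 / 60 = 83%.

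This assumes no lag between enrollment and SCD start, which the document does not state. An assumed lag of 1 to 2 days gives 60 − 10 − 1 = 49 to 60 − 10 − 2 = 48 days. A shorter course lengthens the off-device period. The figure applies to SAEs only: Section 9.7.2 stops non-serious event collection at 120 hours after SCD treatment, or earlier at ICU discharge, death or withdrawal of consent. It measures a window, not a number of events.

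**The case against.** The strongest reply is that little depends on this scale. No endpoint or stopping rule in the document is tied to Definitely or Probably. Section 9.7 reports events per time of device exposure. The mortality comparison counts all causes. Section 7.2 leaves SCD-related discontinuation to the investigator's clinical assessment. The DSMB also sees incidence, severity and timing, at least quarterly. All of this stands, and it confines the defect to the relatedness rating and what is summarized from it.

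A second reply is that a clinically reasonable response is undefined, so a lenient investigator could rate an irreversible or late event higher. That also stands: the bar follows from the literal text. But ratings would then depend on how each site reads the phrase, in a study of up to 10 children at up to 7 centers.

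Two stronger readings are tempting, and the document does not support them.

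- **A reader might infer that a device-linked death could escape UADE assessment.** Section 9.1 lists death, shock, bleeding, hemolysis and air embolism as anticipated during CRRT. Section 9.4 adds that "Adverse events associated with CRRT or underlying critical illness are also to be considered" anticipated, and Section 9.8 says that "anticipated adverse events should be documented and tabulated but need not be submitted by the sponsor to the FDA as individual reports". But 9.3 does not use the four-level scale; it asks whether the effect was previously identified in nature, severity or incidence in the application. Section 9.8 has the sponsor-investigator apply a reasonable-possibility test with no withdrawal condition. Section 9.7.2 sends every SAE to the coordinating centers within 24 hours whatever its relationship. Section 9.4 gives final review of expectedness to the sponsor-investigator and the DSMB. The separate SCD list in 9.1 contains none of those five terms. What remains is that 9.4 does not say outright that a listed term is still checked against 9.3.
- **A reader might infer that 3.5 to 5 deaths would be misrated**, from 10 × (1 − 0.65) = 3.5 (65% survival, Section 12) and 10 × 0.50 = 5 (about 50% mortality, synopsis). These are expected all-cause deaths. Many would have another explanation and miss the top levels anyway. The 65% also describes registry patients on CRRT for 1 to 7 days, not this 10 to 20 kg population.

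**Conclusion.** The point holds as a defect in the rating scale. Followed literally, 9.5.1 and 9.5.2 exclude deaths, irreversible events, events that resolve on continued SCD, and SAEs that begin after SCD is off. Those with no other explanation have no valid level.

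The number of ratings affected cannot be estimated from the document. It is limited to events that already satisfy timing and have no other cause or only an unlikely one; many late SAEs would fail on timing anyway. The 50-day off-device window is a maximum for a full course and rests on a negligible lag from enrollment.

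All-cause mortality, 24-hour SAE reporting and UADE assessment are unaffected. The correction is still worth making, because safety is the primary objective and re-rating deaths once outcomes are known would be open to challenge.

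**What to change.** 1. In 9.5.1 and 9.5.2, remove withdrawal response from the mandatory conditions. Add a sentence saying that, where the event is reversible and SCD was withdrawn while it was ongoing, the course after withdrawal is weighed as supporting evidence.
2. State that fatal, irreversible and post-treatment events are rated on timing and alternative causes alone. Under item 1 the same follows for events that resolve while SCD continues and for events tied to other protocol-required activity.
3. Confirm that an event with plausible timing and no other explanation now falls under 9.5.1 or 9.5.2, and that the four levels together cover all adverse events. Include 9.5.4 in that check, since it also asks for a likely other explanation.
4. Optionally, add one sentence to 9.4 saying that a term on the CRRT list in 9.1 is still checked against 9.3.

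The cost is a few sentences and brief site retraining, ideally before ratings are assigned. Treatment, sample size and data collection do not change. The small downside is that a few more events may be rated probable or definite.

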9.5.3. POSSIBLY RELATED

A clinical event, including a significant change in a laboratory test, that occurs within a reasonable time sequence in relationship to the SCD treatment or other protocol-related activity that could also be explained by concurrent disease, drugs, chemicals, or procedures. The clinical course after withdrawal of the SCD treatment may be unclear with respect to the contribution of the SCD treatment to the AE.

9.5.4. UNRELATED

An AE, including a significant change in a laboratory test, that occurs with a temporal relationship to the SCD treatment or protocol-required activity that makes an association with the SCD treatment or study activity improbable, and in which other drugs, procedures or underlying disease(s) provide likely explanation.

9.6. SEVERITY – INTENSITY

The intensity of all adverse events should be evaluated using the following definitions:

9.6.1. MILD

An event that requires minimal clinical treatment or an adverse event requiring monitoring but no intervention or treatment; causes slight discomfort.

9.6.2. MODERATE

An event that requires non-routine intervention, (i.e., a new clinical treatment or diagnostic procedure), administered within an hour of the event; causes annoying discomfort.

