- Persistent leucopenia, neutropenia, thrombocytopenia based upon PI's clinical assessment
- Absolute neutrophil count less than 500 mm³ will be an indicator for therapy termination
- Platelet count less than 30,000 mm³ after transfusion of 6 units of platelets

8. Other

Any other reason that the Principal Investigator deems appropriate for discontinuation from the SCD Treatment period must be documented.

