9. SAFETY

9.1. ADVERSE EVENTS

An Adverse Event is any sign, symptom, illness, clinically significant abnormal laboratory value or other adverse medical event that appears for the first time or worsens in a subject during this clinical study, regardless of whether or not it is considered related to the device.

Anticipated adverse events that may occur during CRRT include:

- thrombocytopenia
- hypo- or hypernatremia
- hypo- or hyperkalemia
- hypo- or hypercalcemia
- hypo- or hyperglycemia
- other electrolyte imbalance
- air embolism
- hypotension
- hypertension
- hemolysis
- increased oxygenation requirements
- fatigue
- dyspnea
- muscle spasm
- myalgia
- nausea
- vomiting
- fluid imbalance
- leukopenia
- arrhythmias
- hypothermia
- hyperthermia
- lactic acidosis
- temporary decrease in cardiac output or cardiac index
- disruption of skin integrity
- paresthesia
- tetany
- altered mental status
- bleeding
- shock
- infection
- bacteremia
- laryngospasm
- seizure
- death

Anticipated AEs associated with the addition of SCD to CRRT include:

- neutropenia
- thrombocytopenia
- hypotension
- hypo- or hypercalcemia
- alkalosis
- clotting within the device
- leakage due to cracking or breakage

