9.6.3. SEVERE

An event requiring immediate intervention; causes significant discomfort.

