11. DATA SAFETY MONITORING BOARD

An independent Data Safety Monitoring Board (DSMB) will review safety results over the course of the study on a schedule set by Drs. [name] and [name] and the DSMB. The DSMB will comply with the FDA Guidance: "Guidance for Clinical Trial Sponsors on the Establishment and Operation of Clinical Trial Data Monitoring Committees". The DSMB will be formed to provide scientific and medical feedback for the study.

The DSMB will focus on the following areas:

- Performance* – to assess study conduct and compliance
- Effectiveness* – to assess mortality and dialysis dependency
- Safety* – to assess the incidence, severity, relationship, and timing of adverse events and to identify safety concerns; and
- Context* – to assess the study relative to the AKI literature.

The DSMB will reflect the disciplines and medical specialties necessary to interpret the data from the clinical study and to fully evaluate participant safety. The SCD-PED-02 DSMB will be made up of at least 2 medical practitioners with expertise in AKI and critical care medicine. The DSMB will operate under a charter and will identify prospective data display specifications to conduct independent data reviews. The DSMB will make recommendations to the Sponsor to continue the study as planned or to stop the study due to safety. The DSMB will meet to perform safety evaluations and to provide feedback to the Sponsor Investigator at least quarterly. The DSMB reserves the right to request more frequent evaluations.

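### The adverse event severity grades in section 9.6 leave gaps and overlaps, cite discomfort without saying whether it is required, and give no laboratory criteria, so a profound cytopenia that is only monitored can be graded Mild.

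*Combined protocol and SAP*

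**What the plan says.** Section 9.6 gives one three-grade scale for everything: "The intensity of all adverse events should be evaluated using the following definitions". The grades are:

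- **Mild (9.6.1):** an event that "requires minimal clinical treatment or an adverse event requiring monitoring but no intervention or treatment; causes slight discomfort".
- **Moderate (9.6.2):** a non-routine intervention, meaning a new treatment or diagnostic procedure, "administered within an hour of the event; causes annoying discomfort".
- **Severe (9.6.3):** "An event requiring immediate intervention; causes significant discomfort".

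Section 9.1 counts a "clinically significant abnormal laboratory value" as an adverse event. Its list of effects anticipated from adding the SCD includes neutropenia, thrombocytopenia, calcium disturbance and alkalosis. Section 9.6 gives no numeric laboratory criteria.

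Section 7.2, item 7, states: "Absolute neutrophil count less than 500 mm³ will be an indicator for therapy termination". No severity grade is tied to that value.

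Section 11 asks the DSMB "to assess the incidence, severity, relationship, and timing of adverse events". Safety is the primary objective (section 3.1), and laboratory safety parameters are named safety measures (section 3.2).

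**The concern.** A severity scale applied to all events should give each event exactly one grade, and the grade should track how bad the event was. This one has three weaknesses.

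1. **Timing in Moderate.** Time of treatment is part of that definition, so an event needing new but unhurried treatment falls between the grades.
2. **Discomfort.** It appears in every grade after a semicolon, and the protocol does not say whether it is a requirement, an alternative or a description. A laboratory abnormality may cause none. A young child on a ventilator is poorly placed to report it, and ventilation is one way to qualify under section 5.2, item 7.
3. **No laboratory criteria.** The grade of a low count depends on what was done about it, not on the value.

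Sections 3.2 and 5.1 describe an uncontrolled cohort of up to 10 children at up to 7 centers. Moving one subject from one severity row to another changes that row's subject percentage by at least 1/10 = 10 points. If investigators resolve the ambiguities differently, the severity table partly describes their reading of the scale.

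**Working it through.** The protocol states no figure here to reproduce, so the check is a logical one: does each kind of event receive exactly one grade?

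**Inputs.** Definitions from 9.6.1 to 9.6.3. Five management classes and four discomfort levels (none, slight, annoying, significant) give 5 × 4 = 20 cells.

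**Step 1. Intervention part alone.**

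| Management | Grades met |
|---|---|
| Monitoring only | Mild |
| Minimal treatment | Mild |
| New non-routine intervention, needed and given immediately | Moderate and Severe |
| New non-routine intervention, within one hour but not immediate | Moderate |
| New non-routine intervention, after one hour, not needed immediately | none |

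An immediate intervention is also one given within an hour, hence the overlap.

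**Step 2. Add discomfort under three readings of the semicolon.**

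- *Both parts required.* Graded cells: 2 Mild (monitoring or minimal treatment, each with slight discomfort), 2 for immediate intervention (annoying gives Moderate, significant gives Severe) and 1 for treatment within the hour (annoying). That is 5 graded and 20 − 5 = 15 ungraded, including all 5 cells without discomfort.
- *Intervention only.* Late treatment is ungraded: 1 × 4 = 4. Immediate treatment has two grades: 1 × 4 = 4. The other three classes have one grade: 3 × 4 = 12.
- *Either part sufficient.* Only late treatment without discomfort is ungraded: 1. Cells with more than one grade: 2 (monitoring) + 2 (minimal treatment) + 4 (immediate) + 2 (within the hour) = 10. The rest: 20 − 1 − 10 = 9.

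| Reading | No grade | One grade | More than one |
|---|---|---|---|
| Both required | 15 | 5 | 0 |
| Intervention only | 4 | 12 | 4 |
| Either sufficient | 1 | 9 | 10 |

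No reading gives one grade in all 20 cells.

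**Step 3. A laboratory event without discomfort.** Take a neutrophil count below 500, managed by monitoring.

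- Both required: no grade.
- Intervention only, or either sufficient: Mild.

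If the same event needed immediate intervention, it has no grade under the strict reading and meets both Moderate and Severe under the other two. It is never Mild alone. The protocol does not say whether stopping the SCD counts as an intervention, so the grade after a termination is also open.

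**Step 4. What depends on the grade.** Seriousness is defined separately in 9.2. Reporting within 24 hours follows seriousness (9.7.2), and unanticipated device effects have their own definition (9.3). Discontinuation follows 7.2. The grade is used in the DSMB's review of severity (section 11) and in any severity tabulation.

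**The case against.** The strongest case on the other side is that this is a wording matter with little consequence. Moderate can be read as describing how urgently treatment was needed, not as a stopwatch on staff. Serious events, device effects and terminations are handled by rules that ignore the grade. Laboratory parameters are a separate safety measure with daily values on treatment, so a low neutrophil count is visible whatever grade it carries, and 10 patients can be listed individually. The DSMB works under a charter and display specifications that are not among these documents. Stopping the device at a count below 500 is arguably an intervention, so Mild is not the inevitable grade.

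Most of this stands as a limit on the size of the problem. It does not remove the gap, the overlap or the silence on discomfort and stopping SCD. An urgency-of-need reading would be sensible, but 9.6.2 does not state it.

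A reader might infer more than the documents support:

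- *That the whole scale runs on a one-hour clock.* The limit is in Moderate only.
- *That severe laboratory toxicity in sedated children generally grades as Mild.* Toxicity needing immediate intervention does not. If discomfort is mandatory, a monitored event without discomfort is ungraded, not Mild, so those two results rest on different readings. Sedation is not documented.
- *That many ICU events will be ungradable.* The documents give no frequency for this.
- *That the 13.6% severe share in the earlier US pilot (section 2.4.2) is thereby not comparable.* All 69 + 103 + 27 = 199 events there had a grade, but the scale used is not given and no severity comparison with that study is planned.

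**Conclusion.** The point holds in a limited form and should be corrected. The grades in 9.6 are neither exhaustive nor mutually exclusive under any of the three readings. Discomfort suits neither laboratory events nor ventilated young children. Without laboratory criteria, a cytopenia managed by monitoring alone can be graded Mild at a value that section 7.2 treats as an indicator for ending therapy. That last result assumes that discomfort is not mandatory and that nothing beyond monitoring or minimal treatment was done.

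The damage is to severity tabulations and DSMB displays. A reader might conclude that grave events would go undetected; the documents do not support that, because serious event capture and the termination criteria stand apart from the grade. How many events will be affected cannot be estimated from the documents.

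**What to change.** Revise section 9.6 and the adverse event form:

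1. Delete the one-hour clause and the discomfort clauses.
2. Grade by the urgency and level of intervention the event requires, so that each event has exactly one grade. Mild: none, monitoring only or minimal treatment. Moderate: a new non-urgent treatment or procedure. Severe: urgent intervention or new organ support. Do not use the decision to stop SCD as a grading criterion, since that would again grade by staff action.
3. Grade laboratory events on a prespecified, published numeric toxicity scale suited to critically ill children, read against the baseline taken within 12 hours before SCD (section 6.4).
4. State that a value meeting a numeric 7.2 indicator is not graded Mild.
5. Limit laboratory grading to periods with scheduled values. Blood counts, chemistry and liver tests are daily on treatment (6.5). After SCD, blood counts and chemistry are listed for the first 24 hours only, without liver tests (6.6.1), while non-serious events are recorded for up to 120 hours (9.7.2). Blood gas is required only with invasive ventilation and an arterial line (6.3, footnote 8).

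The cost is rewording, a form change and some programming. No treatment, visit or sample changes. Some events will move to a higher grade, and severity counts will not be directly comparable with earlier SCD studies if those used a different scale.
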